5.1.5 Other Prespecified Outcomes Measures

Descriptive analyses of other pre-specified outcome measures beyond the primary and secondary objectives will be exploratory in nature and are not intended as a focus of the study for the evaluation of the study device.

The following will be collected as applicable:

- Rate of positive surgical margins
- Lymph node yield
- Warm ischemia time
- Surgeon experience

6. Study Design

A prospective, multicenter, single-arm pivotal study will be performed in up to 141 subjects undergoing a urologic RAS procedure using the Medtronic Hugo™ RAS System. Subjects without an oncologic indication will be followed for 30 days (+7 days) post procedure. Oncologic subjects will be followed through 5 years. This study will be conducted using up to six investigative sites in the United States of America (USA).

This study will have two phases, a roll-in phase and an open enrollment phase.

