10.1.5 Post-Operative Follow-Up Visits (Visit 4-8)

Post-operative visits 4-8 for oncologic subjects will be made via a phone call to assess overall survival, progression-free survival, and disease-free survival.

Medtronic Expand URO Clinical Investigation Plan

MDT19051EINURO

Version 9.0

Page 40 of 111

Medtronic

Table 6. Data Collection and Study Procedure Requirements at Subject Visits

Procedure/Assessment	Screening (Day -30 to 0) Visit 1	Surgical Procedure (Day 0) Visit 2	Hospital Discharge Visit 2.1	Follow-Up (30+7 Days) Visit 3	Follow-up (Years 1 - 5) (+/- 3 mo. window) Visits 4-8
	May be Combined				
Informed Consent Form ¹	X	X			
Eligibility Criteria	X	X			
Demographic Data	X				
Medical/Surgical History	X				
Concomitant Medication(s)	X	X	X	X	
Lab Values (if applicable)	X	X	X	X	
Robot Setup Time		X			
Total Operative Time (skin to skin)		X			
Surgeon Console Time		X			
Instruments Used		X			
Estimated Blood Loss		X			
Transfusion ³		X	X	X	
Conversion to a robotic-assisted approach utilizing an FDA cleared robotic-assisted device, open or manual laparoscopy		X			
Robot Take Down Time		X			
Warm Ischemia Time (if applicable)		X			
Anastomotic Leak Test performed (if applicable)		X			
Anastomotic Stricture (if applicable)		X			
Rate of Positive Circumferential Margins on Final Pathology (if applicable)		X			
Margin (mm) (if applicable)			X		

Medtronic Business Restricted

This document is electronically controlled

CONFIDENTIAL 056-F275 Rev E Clinical Investigation Plan Template

Medtronic Expand URO Clinical Investigation Plan

MDT19051EINURO

Version 9.0

Page 41 of 111

Medtronic

Procedure/Assessment	Screening (Day -30 to 0) Visit 1	Surgical Procedure (Day 0) Visit 2	Hospital Discharge Visit 2.1	Follow-Up (30+7 Days) Visit 3	Follow-up (Years 1 - 5) (+/- 3 mo. window) Visits 4-8
Tumor Size (if applicable)			X		
Tumor Stage (if applicable)			X		
Total number of lymph nodes retrieved			X		
Catheterization Time			X	X	
Mortality			X	X	X
Length of Hospital Stay			X		
Reoperation			X	X	X
Pain Medication			X	X	
Medications if associated with an AE	X	X	X	X	X
Adverse Events ²	X	X	X	X	X
Readmission				X	X
Device Accountability		X			
Device Deficiency		X			
Protocol Deviation Collection (if applicable)	X	X	X	X	X
Study Exit				X	X

¹Study specific procedures may only be performed after subject has agreed to participate and signed the informed consent form.

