10.9.1 Study Exit

A study exit eCRF is required for all subjects. Prior to exiting a subject from the study, it is recommended

to follow the subject until all ongoing system and/or procedure related AEs are resolved or unresolved with no further actions planned.

Following exit, subjects will continue to receive standard medical care. Upon exiting from the study, no further study data will be collected, or study visits will occur for the subject. All data available through the time of the subject's exit will be used for analysis.

Subjects are urged to remain in the study as long as possible but may be exited from the study for any of the following situations:

- Study completed
- Subject lost to follow-up
- Subject death
- Subject did not meet inclusion/exclusion criteria
- Subject did not provide consent (or data use protection authorization)
- Subject chooses to withdraw (e.g., consent withdrawal, relocation to another geographic location)
- Investigator deems withdrawal necessary (e.g., medically justified, inclusion/exclusion criteria not met, failure of subject to maintain adequate study compliance)

The following information is required to be collected at study exit:

- Reason for exit

If discontinuation is because of safety or lack of effectiveness, the subject shall be asked to be followed for collecting safety data outside the clinical investigation.

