10.9.2 Study Completed

At the completion of the 30 (+7) day follow-up visit, non-oncologic subjects will be exited from the study. At the completion of the 5-year follow-up visit, oncologic subjects will be exited from the study. The 30 (+7) day or the 5-year follow-up visit and exit visit should be combined, and either the 30 (+7) or the 5-year follow-up eCRF and the Study Exit eCRF need to be completed.

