7.9.3.5 Analysis Methods

Secondary objectives 1, 4, 5, 7, 8, 9 and 10 will be summarized by surgery as the count and proportion of subjects experiencing the given endpoint, with a 95% confidence interval.

Secondary objectives 2, 3 and 6 will be summarized by surgery performed using mean, standard deviations (SD), median, IQR, and range. A 95% confidence interval will also be calculated.

Secondary objectives 11, 12 and 13 will be evaluated through separate Kaplan-Meier analyses by surgery.² The event for each Kaplan-Meier will be their respective objective endpoint. Subjects will be censored upon study completion (5-year follow-up visit) or they are lost to follow-up without event. For subjects that are lost to follow-up, their last visit date or date of last subject contact will be used as their censor date, whichever occurred later. The 5-year survival will be estimated from the Kaplan-Meier model and a 95% confidence interval will be calculated.

Secondary objective 1 will have three additional exploratory analyses wherein the overall complication rate within 30 days will be limited to each of: related to device, related to procedure, and related to underlying condition. Relatedness in this exploratory analysis will be any rating other than “Not Related” or equivalent.

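### The Year-5 call may be made from month 57 and ends participation, so compliant subjects can leave up to 3 months before the point at which 5-year OS, PFS and DFS are estimated

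*Protocol*

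**What the plan says.** - **Window.** Protocol section 10.1.5, Table 6, heads the long-term column "Follow-up (Years 1 - 5) (+/- 3 mo. window) Visits 4-8". Study Exit is ticked in the same column.
- **Purpose of the calls.** "Post-operative visits 4-8 for oncologic subjects will be made via a phone call to assess overall survival, progression-free survival, and disease-free survival" (Protocol 10.1.5).
- **Exit.** "At the completion of the 5-year follow-up visit, oncologic subjects will be exited from the study" (Protocol 10.9.2). The same section adds: "The 30 (+7) day or the 5-year follow-up visit and exit visit should be combined". The trigger is the visit, not the 60-month date.
- **After exit.** "Upon exiting from the study, no further study data will be collected, or study visits will occur for the subject" (Protocol 10.9.1). Protocol 10.9.3 asks for vital status to be confirmed in subjects lost to follow-up, but nothing similar is asked for completers.
- **Analysis.** "Subjects will be censored upon study completion (5-year follow-up visit) or they are lost to follow-up without event" and "The 5-year survival will be estimated from the Kaplan-Meier model and a 95% confidence interval will be calculated" (SAP 7.9.3.5).
- **Event dating.** SAP 7.9.3.1, endpoints 12 and 13, places progression and recurrence at the follow-up visit or the last contact, whichever comes first. For OS, time runs to the death itself.
- **Intent.** "Oncologic subjects will be followed through 5 years" (Protocol section 6, opening paragraph). No text sets a lower limit on the date of the Year-5 call.

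**The concern.** The quantity to be estimated is survival at 60 months, yet follow-up of a fully compliant subject may stop at 57. For such a subject, status at 5 years is never observed, and the protocol offers no route to recover it after exit. The 30-day visit does not have this gap, because its window runs only forward (30 +7 days).

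At stake is whether the 5-year values, which Protocol 14.5 sets beside 5-year benchmarks, rest on subjects actually followed to 5 years. If a cohort's calls were mostly made in the first half of the window, few or no subjects would be at risk at 60 months. The reported figure would then be an earlier value carried forward, and the SAP does not say how the 5-year value is read in that case.

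**Working it through.** The plan states no figure for this point, so there is nothing to reproduce. What follows is window arithmetic and an illustration of size.

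**1. Window.** 5 years = 60 months. Earliest compliant Visit 8: 60 - 3 = 57 months. Latest: 60 + 3 = 63 months.

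**2. Inputs for the illustration.** Literature 5-year OS from Protocol 14.5: cystectomy 0.645, nephrectomy 0.931, prostatectomy 0.954. Planned maximum cohort sizes: 31, 55 and 55. Assumptions not in the documents: constant hazard, every subject oncologic, no loss before Visit 8. Real long-term cohorts will be smaller, because only oncologic subjects are followed to 5 years.

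**3. Simulated Kaplan-Meier at 60 months** (3,000 cohorts per cell):

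| Cohort | Calls | Mean at risk at 60 months | Mean estimate |
|---|---|---|---|
| Cystectomy | spread over 57-63 | 9.9 | 0.644 |
| Cystectomy | spread over 60-63 | 20.0 | 0.645 |
| Cystectomy | all at 57 | 0 | 0.660 |
| Nephrectomy | spread over 57-63 | 25.6 | 0.931 |
| Nephrectomy | spread over 60-63 | 51.1 | 0.930 |
| Nephrectomy | all at 57 | 0 | 0.934 |
| Prostatectomy | spread over 57-63 | 26.3 | 0.954 |
| Prostatectomy | spread over 60-63 | 52.5 | 0.954 |
| Prostatectomy | all at 57 | 0 | 0.956 |

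With even spread, the number at risk halves and the estimate does not move.

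**4. Precision.** For cystectomy at n = 27 (31 less 10% attrition), the simulated standard error is 0.091 with calls over 57-63 months and 0.090 over 60-63. That difference is simulation noise: the binomial value with complete follow-up is √(0.645 × 0.355 / 27) = 0.092. For nephrectomy at n = 49 it is about 0.035 under both windows.

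**5. Extreme case.** If every call is at month 57, the carried-forward curve estimates S(57) = S(60)^(57/60):

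- Cystectomy: 0.645^0.95 = 0.659, overstated by 1.4 points.
- Nephrectomy: 0.931^0.95 = 0.934, overstated by 0.3 points.
- Prostatectomy: 0.954^0.95 = 0.956, overstated by 0.2 points.

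Over all survival levels, x^0.95 - x peaks at 0.019 (at x = 0.36), so under a constant hazard the overstatement cannot exceed 1.9 points.

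**6. PFS and DFS under the SAP dating rule.** An event first found at a call is dated to that call or the last contact. If Visit 8 can only fall after month 60, an event found there and dated to the call lands beyond 60 months and drops out of the 5-year estimate, which then approximates the 4-year value. Take an assumed true 5-year PFS of 0.50, visit-dated events only and n = 27. The simulated mean is 0.53 under the current window (+3 points) and 0.58 under a 60-63 month window (+8 points). A hand check of the latter: 0.50^(48/60) = 0.574. Moving the window without changing the dating rule therefore increases the bias in two of the three endpoints.

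**The case against.** The strongest case against is that nothing of consequence follows. Kaplan-Meier treats the early exits as censoring, and precision depends on the risk sets at event times, not on the count at month 60. An empty risk set needs every event-free subject, across up to six sites, to be called in the first half of the window. Even the 1.4-point extreme is small beside a 95% half-width of about 1.96 × 0.092 = 18 points, and beside the gap between the cystectomy OS goal of 35% and the expected 64.5%. The endpoints carry no hypothesis test, and study success depends only on the primary endpoints. A symmetric window is ordinary for annual phone calls feeding a time-to-event analysis, so the contrast with the 30-day visit, which serves a fixed-day binary endpoint, is limited.

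Most of this stands, and it sets the size of the point. A reader might infer from the halved number at risk that 5-year OS is materially biased or imprecise; steps 3 and 4 show otherwise. A reader might also infer a threat to the trial's conclusions; Protocol 14.1 and 14.5 and SAP 7.9.3 rule that out.

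What the objection does not remove is the mismatch itself. The stated intent to follow through 5 years sets no lower limit on the call, and no other text does.

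**Conclusion.** The gap is real and minor. Compliant event-free subjects can be exited and censored up to 3 months before the time point at which OS, PFS and DFS are estimated. With calls spread evenly, OS is practically unbiased and its standard error effectively unchanged. The exposure is a very small or empty risk set at 60 months if calls cluster early, costing at most about 1.4 points for cystectomy OS at the literature mean. These sizes assume a constant hazard, all subjects oncologic and no earlier loss; the PFS figures also assume a true value of 0.50 and visit-dated events.

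The documents do not support reading this as making the 5-year values generally inestimable: that needs all calls in a cohort to fall before month 60. Nor do they support treating a later window as sufficient on its own, given how the SAP dates progression and recurrence.

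**What to change.** Make both changes together, before Visit 8 calls begin, since nothing can be collected after exit.

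1. **Protocol Table 6, Visit 8 only:** set the window to 60 months -0/+3 months. Leave Visits 4-7 at ±3 months. At Visit 8, record vital and disease status as of the 5-year date, with dates of any death, progression or recurrence.
2. **SAP 7.9.3.1, endpoints 12 and 13:** derive PFS and DFS times from the recorded event date instead of the visit or last-contact date.

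Cost: one table entry, one added data field and one SAP sentence. The latest permitted call stays at month 63 and no visit is added. The downside is a final contact window of 3 months rather than 6, which leaves sites less room to reach a subject before the visit counts as out of window.

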10.2 Subject Screening

Consented subjects will be considered for the study if they meet specified inclusion criteria and none of the exclusion criteria. If the subject is consented prior to the day of surgery, a re-verification of eligibility will be signed off by the PI or sub-I on the day of surgery. The criteria for enrollment must be followed explicitly.

Medtronic Business Restricted

This document is electronically controlled

CONFIDENTIAL 056-F275 Rev E Clinical Investigation Plan Template

10.3 Prior and Concomitant Medications/Therapies

Institutional standard of care (SoC) pre-operative protocols and guidelines are typically in place to manage medications and are not reportable for the purposes of this study. Follow the guidelines below to report medications relevant to this study:

- Report applicable pre-procedure medications if taken within 30 days of the study procedure as listed below
- Pain medication(s) must be reported if given when pain (Clavien-Dindo Grade I or higher – pain exceeds that which is considered within normal limits) is reported as an adverse event (AE)
- Medications given during the procedure and/or post-procedure as treatment or preventative that result in reportable AE should be captured
- Please reference # 3 of the I/E for clarification

For study purposes, reporting of the following drugs are required to evaluate potential adverse events and endpoints.

10.3.1 Anticoagulants Taken within 30 Days Prior to Surgery

Prescription anticoagulants may include:

- warfarin (Coumadin)
- enoxaparin (Lovenox)
- clopidogrel (Plavix)
- ticlopidine (Ticlid)
- aspirin (in many versions)
- non-steroidal anti-inflammatory (NSAIDs) (in many versions)
- dipyridamole (Persantine)

Non-prescription (over-the counter or herbal) anticoagulants may include:

- non-steroidal anti-inflammatory (NSAIDs) (in many versions)
- Vitamin E
- Garlic
- Ginger
- Ginkgo biloba

10.3.2 Monoamine Oxidase Inhibitors (MAOIs) Taken within 30 days Prior to Surgery

MAOIs may include:

- tranylcypromine (Parnate, Sicoton)
- phenelzine (Nardil, Nardelzine)
- isocarbonazid (Marplan)
- rasagiline (Azilect)
- selegiline (Eldepryl, Deprenyl)
- linezolid (Zuvox) (an antibiotic)
- St. John's Wort

In addition to the above, any medication given as a result of a study reported adverse event will be reported. Exclude the reporting of antiemetics, antipyretics, analgesics, diuretics and electrolytes and physiotherapy when given per standard of care procedures and/or within normal limits (dosage and frequency).

10.4 Subject Consent

Informed consent (IC) is defined as a legally effective documented confirmation of a subject's voluntary agreement to participate in a particular study after information has been given and explained to the subject on all aspects of the study that are relevant to the subject's decision to participate. This process includes obtaining an IC form that has been approved by the study site's IRB and signed and dated by the subject. A subject may only consent after information has been given and explained to the subject on all aspects of the clinical investigation that are relevant to the subject's decision to participate.

Prior to enrolling subjects, the IC site must be approved by the IRB. The document(s) must be controlled (i.e., versioned and/or dated) to ensure it is clear which version(s) were approved by the IRB. Any adaptation of the sample IC must be reviewed and approved by Medtronic and the IRB reviewing the application prior to enrolling subjects.

The Investigator must notify the subject of any significant new findings about the study that become available during the course of the study which are pertinent to the safety and well-being of the subject, as this could impact a subject's willingness to participate in the study. If relevant, consent may be requested from subjects to confirm their continued participation.

Subjects will be informed that despite signing informed consent, the screening assessment may demonstrate the subject is not a suitable candidate for the study or the procedure and may be withdrawn. Subjects will also be informed that after the investigation visits are completed, the subjects will receive the standard medical care, just as they would have had they not participated in the study.

Medtronic Business Restricted

This document is electronically controlled

CONFIDENTIAL 056-F275 Rev E Clinical Investigation Plan Template

Prior to initiation of any study-specific procedures, IC must be obtained from the subject. The informed consent form must be personally signed and dated by the subject themselves and Investigator or the Investigators designee at the time of consent. Likewise, privacy or health information protection regulation may require subjects to sign additional forms to authorize study sites to submit subject information to the study sponsor.

The IC process must be conducted by the Principal Investigator or an authorized designee, and the IC Form must be given to the subject in a language he/she is able to read and understand. The process of IC must be conducted without using coercion or undue improper influence on or inducement of the subject to participate by the Investigator or other study site personnel. The IC process shall not waive or appear to waive subject's legal right. The language used shall be as non-technical as possible and must be understandable to the subject.

The subject must have ample time and opportunity to read and understand the IC form, to inquire about details of the study, and to decide whether or not to participate in the study. All questions about the study should be answered to the satisfaction of the subject.

When the subject decides to participate in the study, the IC must be signed and personally dated by the subject and Investigator or authorized designee, as required by the IC, and ensured by the Principal Investigator or his/her authorized designee.

A copy of the IC signed and dated as required by law, must be provided to the subject.

If the IC is obtained the same day the subject begins participating in study-related procedures, it must be documented in the subject's case history that consent was obtained prior to participation in any study-related procedures. It is best practice for the IC process to be documented in the subject's case history, regardless of circumstance.

10.5 Assessment of Performance

The secondary endpoints of this study (operative time, device-related conversions, device deficiencies) will assess the overall performance of the Medtronic Hugo™ RAS System when used for urologic robotic surgery. Secondary endpoints will evaluate the safety and performance of the study device and will not evaluate specific label claims.

10.6 Assessment of Safety

Safety will be evaluated through the study primary endpoint (major complications) and several secondary endpoints (**Section 5.1.4**).

Safety will also be assessed by monitoring the occurrence of adverse events (AEs), serious adverse events (SAEs), deaths, adverse device effects (ADE), serious adverse device effects (SADE), unanticipated adverse device effects (UADE) or device deficiencies. Adverse event assessments will take place starting with the point of consent, through the end of study exit through 5-year follow-up, or until resolution whichever comes first and will be recorded in the eCRF.

Medtronic Business Restricted

This document is electronically controlled

CONFIDENTIAL 056-F275 Rev E Clinical Investigation Plan Template

AEs will be collected from the time of consent. AEs occurring in subjects excluded from the full analysis set (FAS) (**Section 14.1**) will be followed post-consent through study exit and will be reported in a listing in the clinical study report (CSR).

These AEs will not be included in the FAS summary analysis for either AE reporting or the analysis of the primary and secondary endpoints.

For the FAS, the type, incidence, severity, duration, and procedure/device relatedness of AEs will be reported. AEs for all FAS subjects will be analyzed from first incision through the study exit.

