12.1 Adverse Events

All Adverse Events (AEs) will be collected, starting from the time the informed consent form is signed through 30 days (+7) after the day of the procedure regardless of their severity or relationship to the Hugo™ RAS or study procedures. After 30 days, AEs will be assessed by the surgeon and those AEs deemed attributable to the underlying surgical indication, procedure or surgical device will be reported. All deaths will be collected via AE regardless of relatedness. Reporting of these events to Medtronic will occur on an AE Form, including event description, date of AE, treatment, resolution, assessment of both the seriousness of the AE and the relatedness to the system components. Each AE must be recorded on a separate AE eCRF.

AE definitions used in this study are based on ISO 14155:2020 (Clinical Investigation of Medical Devices for Human Subjects -- Good Clinical Practice). Documented pre-existing conditions are not considered AEs unless the nature or severity of the condition has worsened. See **Section 14.1** for details regarding AE analyses in each study analysis set. In addition, AEs impacting users or other persons (non-subject AEs) will be collected on a non-subject AE CRF.

Any unresolved procedural or device-related events that are still ongoing past study exit will be monitored by the physician per their institutional standard-of-care.

Unavoidable adverse events (UAE) (those that are inherent to the procedure and are expected to occur in all subjects for an expected duration) listed in **Table 9** will not be captured or reported unless the adverse event worsens or persists outside the stated timeframe post procedure. **Section 11.1** includes a list of several, but not an all-encompassing anticipated adverse events.

All deaths, serious adverse events related to the Hugo™ RAS System and/or study procedures and Clavien-Dindo Grade III and IV complications will be adjudicated by an independent CEC.

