14.9 Analysis Populations

The following populations will be considered for the analysis of data for this study:

Full Analysis Set

The full analysis set (FAS) is defined as all enrolled subjects in whom the Hugo™ RAS procedure is begun, defined as the first skin incision. This is also known as a modified intent-to-treat (mITT) population. In the event that a subject is consented, but the first incision does not occur (e.g., if the subject becomes ineligible during the timeframe between consent and the procedure day), that subject will not be considered part of the FAS. The FAS will be the primary analysis set for the evaluation of the primary and secondary endpoints.

AEs will be collected from the time of consent. AEs occurring in subjects excluded from the FAS will be followed for 30 days post-consent through study exit and will be reported in a listing in the clinical study report. These AEs will not be included in the primary FAS analysis for either AE reporting or the analysis of the primary and secondary endpoints. The number and proportion of subjects experiencing each type of adverse event will be summarized by site and overall for the FAS.

Per Protocol Analysis Set

The per protocol analysis set (PPAS) is a subset of the FAS including only those subjects without any major protocol deviations. Prior to data analysis, a protocol deviation listing will be produced and sent to the clinical manager/team for review in order to verify which subjects will be excluded from the PPAS. Reasons for exclusion of subjects from PPAS will be documented and reported.

All enrolled subjects will be included in a subject disposition table indicating reasons for exclusion from the FAS and PPAS analysis sets.

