7.1.3 Analysis Sets

The following populations will be considered for the analysis of data for this study:

Full Analysis Set

The full analysis set (FAS) is defined using the modified intent-to-treat (mITT) principle as all enrolled subjects for whom a Hugo™ RAS procedure was begun, with the beginning of a procedure defined as the first skin incision being made. In the event that a subject is consented, but the first incision does not occur (e.g., if the subject becomes ineligible during the timeframe between consent and the procedure day), that subject will not be considered part of the FAS. The FAS will be the primary analysis set for the evaluation of the primary and secondary endpoints.

Adverse Events (AEs) will be collected from the time of consent. AEs occurring in patients excluded from the FAS will be followed for 30 days post-consent through study exit and will be reported in a listing in the CSR. These AEs will not be included in the primary FAS analysis for either AE reporting or the analysis of the primary and secondary endpoints. The number and proportion of subjects experiencing each type of AE will be summarized by site, surgery type and overall for the FAS.

Per Protocol Analysis Set

The per protocol analysis set (PPAS) is a subset of the FAS including only those subjects without any major protocol deviations. Major deviation reasons are: "Enrolled subject did not meet enrollment criteria" and

“Unauthorized use of investigational device.” Reasons for exclusion of subjects from PPAS will be documented in tabular format and reported.

All enrolled subjects will be included in a subject disposition table indicating reasons for exclusion from the FAS and PPAS analysis sets.

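### The AE and SAE tables run to study exit as crude proportions, pooling 30-day with 5-year follow-up and two collection rules, so they cannot be compared across sites, surgery types or data cuts

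*Protocol*

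**What the plan says.** **Window.** Protocol section 10.6 (and the Synopsis) says "AEs for all FAS subjects will be analyzed from first incision through the study exit".

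**Exit.** Protocol section 6: "Subjects without an oncologic indication will be followed for 30 days (+7 days) post procedure", whereas "Oncologic subjects will be followed through 5 years". Section 10.9.2 confirms that these are the exit points.

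**Measure.** Protocol section 14.9: "The number and proportion of subjects experiencing each type of adverse event will be summarized by site and overall for the FAS". SAP section 7.1.3 adds surgery type: "The number and proportion of subjects experiencing each type of AE will be summarized by site, surgery type and overall for the FAS". SAP section 7.10 presents frequencies of ADEs, SAEs, SADEs and UADEs in tables and listings. It gives no time window and no exposure measure.

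**Collection.** Under Protocol section 12.1, AEs up to 30 days (+7) are collected "regardless of their severity or relationship to the Hugo™ RAS or study procedures". The rule then narrows: "After 30 days, AEs will be assessed by the surgeon and those AEs deemed attributable to the underlying surgical indication, procedure or surgical device" are reported. The same section adds that every death is collected as an AE whatever its relatedness, and section 12.4 repeats this for unrelated deaths after day 30.

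**Late contact.** Protocol section 10.1.5: "Post-operative visits 4-8 for oncologic subjects will be made via a phone call to assess overall survival, progression-free survival, and disease-free survival".

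**Timing.** The clinical study report follows once all subjects have completed 30 days or exited; the 5-year results go into a separate final report (Protocol section 14.2, SAP section 7.2).

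**The concern.** A proportion of subjects with an event has a clear meaning only when everyone is observed for the same time under the same reporting rule. Neither condition holds here. A subject followed for 5 years has much longer to enter the numerator than one who leaves at day 30 to 37, yet each counts once in the denominator. For AEs and SAEs, an unrelated non-fatal event counts on day 20 but not on day 200.

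The tables are to be shown by site and by surgery type, and readers will compare the columns. Differences could arise from the mix of oncologic and non-oncologic subjects, or from how long ago each site began operating, with no difference in operative risk. Roll-in cases come from two sites only and are kept in the analysis (Protocol section 6.1). At the 30-day report, oncologic subjects at those sites will tend to have the longest follow-up.

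No other section settles this. Protocol section 12.1 points to section 14.1 for AE analysis details, but section 14.1 contains none. The SAP fixes a 30-calendar-day window for the 30-day endpoints but not for the AE tables.

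**Working it through.** The plan gives no AE incidence to study exit, so there is no figure to reproduce. The check is how far the planned proportion moves when the 30-day risk is held constant.

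**Inputs from the documents**
- Follow-up: 30 (+7) days or 5 years (Protocol section 6).
- 30-day risk p = 0.116, the literature mean for any complication after nephrectomy (Protocol section 14.5), used as a stand-in for AE risk. The cystectomy mean, 0.417, is a second case.
- Literature mean 5-year overall survival: 0.931 nephrectomy, 0.954 prostatectomy, 0.645 cystectomy (Protocol section 14.5).

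**Assumptions, not in the documents**
- Oncologic share f: 0.5 to 0.9.
- Rate h of a first reportable event after day 30, in subjects with none before: 0.02 to 0.10 per year, constant.
- Complete follow-up of oncologic subjects to the stated time.

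**Step 1: follow-up ratio.** 5 / (30/365.25) = 60.9. Against day 37 it is 1826/37 = 49.

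**Step 2: pooled proportion to exit.** With T = 5 − 30/365.25 = 4.918 years:

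P = f × [1 − (1 − p) × exp(−h × T)] + (1 − f) × p

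For p = 0.116, f = 0.5, h = 0.02: 0.5 × [1 − 0.884 × exp(−0.0984)] + 0.5 × 0.116 = 0.157.

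| p | f | h = 0.02 | h = 0.05 | h = 0.10 |
|---|---|---|---|---|
| 0.116 | 0.5 | 15.7% | 21.2% | 28.8% |
| 0.116 | 0.9 | 19.1% | 28.9% | 42.5% |
| 0.417 | 0.5 | 44.4% | 48.1% | 53.0% |
| 0.417 | 0.9 | 46.6% | 53.1% | 62.1% |

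Two sites with the same 11.6% 30-day risk and the same 5% yearly rate, but 50% and 90% oncologic subjects, would show 21.2% and 28.9%.

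**Step 3: dependence on the data cut.** With p = 0.116, f = 0.9, h = 0.05, and T replaced by t − 30/365.25, where t is the oncologic follow-up at the cut:

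| t | 30 days | 1 year | 2 years | 5 years |
|---|---|---|---|---|
| P | 11.6% | 15.2% | 18.9% | 28.9% |

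**Step 4: deaths alone.** All deaths are AEs (Protocol section 12.1), and an AE leading to death is serious (Table 7). If oncologic subjects match the literature means, deaths alone put these shares of them into the SAE table by 5 years: cystectomy 1 − 0.645 = 35.5%, nephrectomy 1 − 0.931 = 6.9%, prostatectomy 1 − 0.954 = 4.6%. Non-oncologic deaths count only to day 30 to 37.

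**Step 5: fixed window.** Restricted to day 30, P = p = 11.6% for every f, h and t above.

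**The case against.** The strongest reply is that the decision-relevant safety rates already have a fixed window. The SAP uses 30 calendar days for major complications (section 7.9.2.2) and for overall complications, transfusion, readmission, reoperation and mortality (section 7.9.3.1). It also breaks major and overall complications down by relatedness to device, procedure and underlying condition (sections 7.9.2.7 and 7.9.3.5). The AE tables are descriptive, carry no performance goal and do not enter the success rule in Protocol section 14.1. All of this stands. A reader might infer that the trial's safety rates as a whole cannot be interpreted, or that the primary safety result is compromised; the documents support neither.

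A reader might also infer that the change of rule distorts the ADE and SADE tables. It does not: device- and procedure-attributed events are reportable before and after day 30. Those tables are affected only by unequal follow-up and by late contact being a telephone call aimed at survival and disease status.

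It is also fair that the oncologic share is not stated. Protocol section 6.4.2 describes the three operations as high-volume oncologic surgeries, although section 9.1 allows non-oncologic diagnoses. If nearly all subjects are oncologic, the 30-day versus 5-year contrast carries little weight. The change of rule and the staggered follow-up at the 30-day report would remain.

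Finally, an all-AE table cut at day 30 would still differ from the primary safety endpoint, which counts related Grade III or higher events using adjudicated relatedness. Making the two agree is not a reason for the change.

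**Conclusion.** The point holds for the AE and SAE tables. As specified, their proportions are not comparable across sites, surgery types or data cuts. ADE and SADE tables share the unequal follow-up and the weaker late ascertainment, but not the change of rule. The 30-day primary and secondary endpoints and the hypothesis tests are untouched.

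The size cannot be fixed from the documents. With a 30-day risk of 11.6%, 50% to 90% oncologic subjects and 2% to 10% per year later first events, the pooled proportion at the end of 5-year follow-up would be about 16% to 43%. The oncologic share and late rate are assumptions, and the upper values need complete 5-year follow-up, so they describe the final report rather than the 30-day report. For the latter, the excess over the 30-day risk depends on the follow-up accrued at the cut.

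A reader might conclude that differences between columns will reflect case mix and not the device. That is not shown: the plan leaves the two inseparable in these tables.

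**What to change.** Amend Protocol sections 10.6 and 14.9 (with the matching Synopsis sentence) and SAP sections 7.1.3 and 7.10:

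1. Make the main AE, SAE, ADE and SADE tables cover first incision through day 30 in the whole FAS, by site, surgery type and overall.
2. Report later events in separate tables for oncologic subjects, per person-year or as cumulative incidence, labelled *attributable events plus all deaths*. A label of attributable events alone would be wrong, because unrelated deaths are included. List any events in non-oncologic subjects between day 31 and exit, so that none is lost.
3. State the data cut for each report.
4. Reconcile Protocol sections 12.1 and 12.4, which put full collection at 30 days (+7) but start the narrower rule after 30 days, so that it is clear whether the rule changes at day 30 or day 37. A main table ending at day 30 lies within full collection on either reading.

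The cost is wording and one additional split of existing tables. No new data are needed: procedure and AE start dates already define the primary safety endpoint (SAP section 7.9.2.2), and last-contact dates are already used for censoring (SAP section 7.9.3.5).
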